16.4 Data & Safety Monitoring

16.41 The principal investigator(s) and the study statistician will review the study at least twice a year to identify accrual, adverse event, and any endpoint problems that might be developing. The Mayo Clinic Cancer Center (MCCC) Data Safety Monitoring Board (DSMB) is responsible for reviewing accrual and safety data for this trial at least twice a year, based on reports provided by the MCCC Statistical Office.

16.42 Adverse Event Stopping Rule: The stopping rule specified below is based on the knowledge available at study development. We note that the Adverse Event Stopping Rule may be adjusted in the event of either (1) the study re-opening to accrual or (2) at any time during the conduct of the trial and in consideration of newly acquired information regarding the adverse event profile of the treatment(s) under investigation. The study team may choose to suspend accrual because of unexpected adverse event profiles that have not crossed the specified rule below.

Accrual will be temporarily suspended to this study if at any time we observe events considered at least possibly related to study treatment (i.e., an adverse event with attribute specified as "possible", "probable", or "definite") that satisfy the following:

- if 4 or more patients in the first 20 treated patients (or 20% after 20 patients have been accrued) experience a Grade 4 or higher non-hematologic adverse event.

We note that we will review Grade 4 and 5 adverse events deemed "unrelated" or "unlikely to be related", to verify their attribution and to monitor the emergence of a previously unrecognized treatment-related adverse event.

- 16.5 Results Reporting on ClinicalTrials.gov: At study activation, this study will have been registered within the “ClinicalTrials.gov” website. The Primary and Secondary Endpoints (ie, “Outcome Measures”) along with other required information for this study will be reported on ClinicalTrials.gov. For purposes of timing of the Results Reporting, the initial estimated completion date for the Primary Endpoint of this study is 22 months after the study opens to accrual. The definition of “Primary Endpoint Completion Date” (PECD) for this study is the time that every patient has either completed 4 cycles of treatment or ended active treatment (whichever occurs first).
- 16.6 Inclusion of Women and Minorities
- 16.61 This study will be available to all eligible patients, regardless of race, gender, or ethnic origin.
- 16.62 There is no information currently available regarding differential effects of this treatment regimen in subsets defined by race, gender, or ethnicity, and there is no reason to expect such differences to exist. Therefore, although the planned analysis will, as always, look for differences in treatment effect based on racial and gender groupings, the sample size is not increased in order to provide additional power for subset analyses.
- 16.63 Based on prior MCCC studies involving similar disease sites, we expect about 4% of patients will be classified as minorities by race and 50% of patients will be women. Expected sizes of racial by gender subsets are shown in the following table:

Accrual Targets			
Ethnic Category	Sex/Gender		
	Females	Males	Total
Hispanic or Latino	1	1	2
Not Hispanic or Latino	14	14	28
Ethnic Category: Total of all subjects	15	15	30
Racial Category			
American Indian or Alaskan Native	0	0	0
Asian	0	0	0
Black or African American	1	1	2
Native Hawaiian or other Pacific Islander	0	0	0
White	14	14	28
Racial Category: Total of all subjects	15	15	30

Ethnic Categories: **Hispanic or Latino** – a person of Cuban, Mexican, Puerto Rican, South or Central American, or other Spanish culture or origin, regardless of race. The term “Spanish origin” can also be used in addition to “Hispanic or Latino.”

Not Hispanic or Latino

Racial Categories:

American Indian or Alaskan Native – a person having origins in any of the original peoples of North, Central, or South America, and who maintains tribal affiliations or community attachment.

Asian – a person having origins in any of the original peoples of the Far East, Southeast Asia, or the Indian subcontinent including, for example, Cambodia, China, India, Japan, Korea, Malaysia, Pakistan, the Philippine Islands, Thailand, and Vietnam. (Note: Individuals from the Philippine Islands have been recorded as Pacific Islanders in previous data collection strategies.)

Black or African American – a person having origins in any of the black racial groups of Africa. Terms such as “Haitian” or “Negro” can be used in addition to “Black or African American.”

Native Hawaiian or other Pacific Islander – a person having origins in any of the original peoples of Hawaii, Guam, Samoa, or other Pacific Islands.

White – a person having origins in any of the original peoples of Europe, the Middle East, or North Africa.

17.0 Pathology Considerations/Tissue Biospecimens**17.1 Summary Table of Research Tissue Specimens to be Collected for this Protocol**

Correlative Study (Section for more information)	Mandatory or Optional	Type of Tissue to Collect	Block, Slides, Core, etc. (# of each to submit)	Baseline	Just prior to Cycle 2, Day 1¹	At Progress ion¹	Process at site? (Yes or No)	Temperature Conditions for Storage /Shipping
Whole Exome Sequencing (WES); Whole Methyome Profiling (RRBS)	Optional	Fresh or Frozen	3-6 cores	X	X	X	No	Freeze.
IHC biomarkers	Optional	Formalin Fixed Paraffin Embedded or fresh	10 of slides	X	X	X	No	Ambient,

1. only if archival specimen was available

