9.0 Ancillary Treatment/Supportive Care

- 9.1 Antiemetics may be used at the discretion of the attending physician.
- 9.2 Blood products and growth factors should be utilized as clinically warranted and following institutional policies and recommendations. The use of growth factors should follow published guidelines of the American Society of Clinical Oncology (42) Update of Recommendations for the Use of Hematopoietic Colony-Stimulating Factors: Evidence-Based, Clinical Practice Guidelines. *J Clin Oncol* July 1, 2006, vol. 24 no. 19 3187-3205.
- 9.3 Patients should receive full supportive care while on this study. This includes blood product support, antibiotic treatment, and treatment of other newly diagnosed or concurrent medical conditions. All blood products and concomitant medications such as antidiarrheals, analgesics, and/or antiemetics received from the first day of study treatment administration until 30 days after the final dose will be recorded in the medical records.
- 9.4 **Vascular Occlusion**

Arterial and venous thrombosis and occlusions, including fatal myocardial infarction, stroke, stenosis of large arterial vessels of the brain, severe peripheral vascular disease, and the need for urgent revascularization procedures have occurred in at least 27% of Iclusig-treated patients from the phase 1 and phase 2 trials. Iclusig can cause fatal and life-threatening vascular occlusion within 2 weeks of starting treatment. Iclusig can also cause recurrent or multi-site vascular occlusion.

The median time to onset of the first vascular occlusion event was 5 months. Iclusig can cause fatal and life threatening vascular occlusion in patients treated at dose levels as low as 15 mg per day.

Patients with and without cardiovascular risk factors, including patients age 50 years or younger, experienced these events. Vascular occlusion adverse events were more frequent with increasing age and in patients with prior history of ischemia, hypertension, diabetes, or hyperlipidemia (see Table 4).

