10.41 Adverse Events of Special Interest (AESIs)

Vascular occlusive events have been identified as AESIs for ponatinib. These include arterial and venous thrombotic and occlusive adverse events that meet the criteria for SAEs (see section 10.1) and those adverse events that do not meet the SAE criteria. AESIs require ongoing monitoring by investigators and rapid identification and communication by the investigator to the study sponsor. All AESIs, whether SAEs or not, must be reported within 2 business days of the study sponsor awareness to ARIAD.

ARIAD has determined that the events listed below (whether considered serious or non-serious by investigators) should be considered AESIs:

- A. Myocardial infarction: The Third Universal Definition of Myocardial Infarction (Thygesen et al, 2012) is used to define MI
- B. Angina (newly diagnosed or worsening of existing angina or unstable angina)
- C. Coronary artery disease (CAD) (newly diagnosed or worsening of existing CAD) or symptoms that may reflect cardiovascular disease (Thygesen et al, 2012)
- D. Cerebrovascular ischemic disease including ischemic or hemorrhagic stroke, vascular stenosis, transient ischemic accident (TIA), cerebrovascular occlusive disease documented on diagnostic neuroimaging, or symptoms that may reflect cerebrovascular disease (Easton et al, 2009)
- E. New onset or worsening of peripheral artery occlusive disease (eg, renal artery, mesenteric artery, femoral artery) or symptoms that may reflect peripheral vascular disease
- F. Retinal vascular thrombosis, both venous and arterial
- G. Venous thromboembolism where significant compromise of organ function or other significant consequences could result (eg, pulmonary embolism, portal vein thrombosis, renal vein thrombosis) or symptoms that may reflect venous thrombosis

ARIAD may request additional information to the study sponsor on observed AESIs and this information should be provided in a timely fashion (ie, within 2 business days of the study sponsor awareness).

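### The only numerical adverse event rule (16.42) leaves out Grade 3 vascular occlusions, the trial's named event of special interest, and has no stated effect once accrual has closed

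*Combined protocol and SAP*

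**What the plan says.** **The rule (16.42).** The opening sentence gives the action, the timing and the attribution: "Accrual will be temporarily suspended to this study if at any time we observe events considered at least possibly related to study treatment". What is counted is the number of patients who "experience a Grade 4 or higher non-hematologic adverse event". The boundary for that count is worded "if 4 or more patients in the first 20 treated patients (or 20% after 20 patients have been accrued"). No vascular or special-interest criterion appears, no action other than suspending accrual is named, and no operating characteristics are given.

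**Discretion around the rule (16.42).** "The study team may choose to suspend accrual because of unexpected adverse event profiles that have not crossed the specified rule below". The rule itself may be adjusted when the study re-opens to accrual, or at any time on new safety information.

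**Status of vascular occlusion.** Section 10.41: "Vascular occlusive events have been identified as AESIs for ponatinib", whether or not they are serious. Section 9.4 says that such events "have occurred in at least 27% of Iclusig-treated patients from the phase 1 and phase 2 trials", and adds: "The median time to onset of the first vascular occlusion event was 5 months". Section 8.2 lists discontinuation for stroke or myocardial infarction of any grade and for a thromboembolic event from Grade 1. Section 1.23 reports a partial clinical hold on new enrolment in October 2013, in the setting of an increased cumulative risk of these events.

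**Other oversight.** Investigators and statistician, and separately the DSMB, review the study at least twice a year (16.41). Adverse events enter any decision to terminate (16.25). Special-interest events go to the drug supplier within 2 business days (10.41).

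**The concern.** The protocol treats vascular occlusion as important at every grade for the individual patient and for reporting, but the trial-level rule sees it only from Grade 4. Several related Grade 3 strokes, infarctions or limb occlusions could accumulate without moving the one quantitative boundary.

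The action raises a second difficulty. Responding and stable patients stay on treatment (13.1), and the stated median onset is 5 months, so part of the vascular risk falls after the last patient has entered. Suspending accrual is then an empty instruction, and nothing in 16.42 says what else follows. What is at stake is how quickly an accumulating signal reaches the DSMB between its scheduled reviews, and whether anyone is required to consider the patients still taking the drug.

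**Working it through.** **1. The plan's own figures.** Accrual (16.22, 16.23): 30 patients / 3 per month + 6-month pause = month 16. Final analysis: 16 + 6 = month 22. Both match the text. The rule's fraction is 4/20 = 20%; 20% then means 5 patients for n = 21 to 25 and 6 for n = 26 to 30.

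**2. How the rule behaves on what it counts.** Exact binomial, P(X ≥ 4 | n = 20, p), where p is the true rate of related Grade 4+ non-hematologic events:

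| p | 5% | 10% | 15% | 20% | 25% | 30% |
|---|---|---|---|---|---|---|
| P(≥ 4 of 20) | 0.016 | 0.133 | 0.352 | 0.589 | 0.775 | 0.893 |

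Grade 3 occlusions contribute zero to X at any frequency. Related Grade 4-5 occlusions do count.

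**3. Illustration of what Grade 3 would add.** The 27% comes from 9.4. The grade split is an assumption, because the documents give none. All occlusions are taken as at least possibly related.

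- Central case, half Grade 3+ and a quarter Grade 4+. Grade 4+: p = 0.27 × 0.25 = 0.0675, giving 0.04. Grade 3+: p = 0.27 × 0.50 = 0.135, giving 0.28.
- Range, with total occlusion 15% to 27%, Grade 4+ share 17% to 30% and Grade 3+ share 33% to 75%. Grade 4+: p from 0.0255 to 0.081, giving 0.0015 to 0.07. Grade 3+: p from 0.0495 to 0.2025, giving 0.02 to 0.60.

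These figures cover vascular events alone. The rule also counts other related Grade 4+ non-hematologic events. With an assumed independent background rate b, the counted rate is 1 − (1 − v)(1 − b), where v is the vascular rate:

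| Background b | Vascular Grade 4+ only (v = 0.0675) | Vascular Grade 3+ (v = 0.135) |
|---|---|---|
| 5% | p = 0.114, P = 0.19 | p = 0.178, P = 0.49 |
| 10% | p = 0.161, P = 0.40 | p = 0.222, P = 0.68 |

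**4. Timing.** With 10 patients in Stage 1, patient 20 enters at 10/3 + 6 + 10/3 = month 12.7. Patients 20 to 30 therefore have at most 16 − 12.7 = 3.3 months of exposure when accrual closes, less than the 5-month median onset. If onset is taken as exponential, the share of a patient's eventual first occlusions that fall after month 16 is exp(−ln 2 × (16 − entry month)/5). Averaged over 30 evenly spaced entries, this is 0.49 (0.37 with a 3-month median, 0.61 with 8 months). It assumes that every patient stays on treatment, so it lies on the high side; stopping at progression lowers it.

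**The case against.** The strongest reply is that 16.42 does not stand alone. The DSMB reviews safety at least twice a year with no link to open accrual, 16.25 lets adverse events bear on termination, 16.22 allows for undue adverse events, and the rule is adjustable. Section 8.2 acts on the individual patient at any grade, although 9.4 speaks of interrupting or stopping, with a benefit-risk decision on restarting, and of considering dose modification for serious venous events; those passages must be reconciled. All this stands, and it rules out any inference that Grade 3 or late events go unmonitored. But none of these provisions sets a vascular threshold or a prompt DSMB trigger.

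Other readings that a reader might infer go too far:

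- *Late events can never meet the rule.* The text applies it at any time, so they can. It is the action that is empty after closure.
- *The rule does nothing in the Stage 1 pause.* Crossing it then gives a separate reason to keep accrual shut, although the text does not spell this out.
- *The discretionary clause cannot reach vascular events because they are listed as known.* The clause concerns profiles, and the note in 10.2 brings in severity and frequency, so an excess could arguably qualify. Against that, 9.4 already discloses at least 27%, and this clause too acts only on accrual.
- *Three of the first 10 patients ought to cross a 20% rule.* The plan sets a fixed count of 4 within the first 20, with a percentage only afterwards. That is a design choice and not an error.
- *The denominator switches to accrued patients.* That word may only mark when the percentage takes over. It is a wording doubt.

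The 27% also comes from earlier trials. This one excludes prior infarction, stroke and revascularization (3.29h) and advises aspirin and a statin (7.3, 7.4), so its rate may be lower.

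**Conclusion.** The point holds as a gap in the formal rule. Two facts follow from the text with no assumption: Grade 3 vascular occlusions never contribute to the only numerical boundary, and crossing that boundary after accrual closes has no stated consequence for patients on treatment.

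The size is less certain. The contrast of 0.04 with 0.28 rests on an assumed grade split and on vascular events alone. It is not the probability that the rule as a whole is crossed, which under the assumed 5% to 10% background is 0.19 to 0.40 as written, against 0.49 to 0.68 with Grade 3 vascular events included. The gap persists across these cases, but its width cannot be fixed from the documents. The period without effect is about six months on the planned timeline (month 16 to month 22), and longer for anyone still on treatment after that.

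The documents do not support a claim that safety oversight is missing or that the trial is unsafe. The amendment is worth making because it is cheap and brings a signal to the DSMB between scheduled reviews.

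**What to change.** Amend 16.42 in three places:

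1. State that crossing the boundary at any time, including while accrual is suspended or closed, triggers a prompt DSMB review that covers patients still on treatment. If it is crossed before Stage 2, the review is completed before Stage 2 opens.
2. Add confirmed Grade 3 or higher vascular occlusive events from the 10.41 list as a separate trigger for DSMB review, leaving out the items defined only by symptoms that might reflect vascular disease. The study team and the DSMB should set the count and tabulate its operating characteristics over a range of true rates.
3. Clarify that the percentage after patient 20 is a percentage of treated patients.

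The second item triggers a review and leaves the accrual-suspension count unchanged, so the existing rule keeps its properties. Whether Grade 3 events should also suspend accrual is a trade-off for the team.

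Cost: one paragraph and no new data collection, since these events are already reported within 2 business days. The downside is more ad hoc reviews, some of them prompted by chance; the tabulation in item 2 would show how many to expect.

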17.2 Correlative Tissue Collection

17.31 Tissue Kits will not be provided for this protocol.

17.32 Paraffin Embedded Tissue

17.321 10 slides per table 17.1

17.322 Shipping and Storage
All samples will be kept at Mayo Clinic Scottsdale campus until lab is ready for processing.

Shipping Specimens
Verify ALL sections of the Specimen Submission Forms are completed and filled in correctly.

Ship specimens via Priority Overnight service, **Monday – Thursday ONLY**, to:

Mayo Clinic

Do not send samples the day before, the day of, or the observed day of a national holiday.

All specimens must be shipped Monday – Thursday ONLY.

17.33 Frozen or Fresh Tissue

17.331 3-6 Cores per section 17.1 timepoints

17.332 Shipping and Storage

All samples will be kept at Mayo Clinic Scottsdale campus until lab is ready for processing.

Shipping Specimens
Verify ALL sections of the Specimen Submission Forms are completed and filled in correctly.

Ship specimens via Priority Overnight service, **Monday – Thursday ONLY**, to:

Mayo Clinic

Do not send samples the day before, the day of, or the observed day of a national holiday.

All specimens must be shipped Monday – Thursday ONLY.

18.0 Records and Data Collection Procedures

18.1 Submission Timetable

Initial Material(s)

CRF	Active-Monitoring Phase (Compliance with Test Schedule Section 4.0)
On-Study	≤14 days after registration
Adverse Event - Baseline	
RECIST Measurement – Baseline	
Concomitant Medication - Baseline	
Hematology Laboratory	
Chemistry Laboratory	
Other Laboratory	
Patient Questionnaire Booklet ¹	
Booklet Compliance ²	
OP and Path Reports (see Section 17.0)	
Research Blood Submission	≤30 days after registration
Research Tissue Submission	
End of Active Treatment/Cancel Notification	Submit ≤2 weeks after registration if withdrawal/refusal occurs prior to beginning protocol therapy

1. Patient questionnaire booklet **must** be used; copies are not acceptable for this submission.
2. This form must be completed only if the patient questionnaire booklet contains absolutely NO patient provided assessment information.

Test Schedule Material(s)

CRF	Active-Monitoring Phase (Compliance with Test Schedule Section 4.0)
	At each evaluation during treatment
Evaluation/Treatment	X ¹
Adverse Event	X

CRF	Active-Monitoring Phase (Compliance with Test Schedule Section 4.0)
	At each evaluation during treatment
RECIST Measurement	X
Concomitant Medication	X
Other Laboratory	X (see Section 4.0)
Hematology Laboratory	X (see Section 4.0)
Chemistry Laboratory	X (see Section 4.0)
Research Tissue Submission	X (see Section 17.0)
Research Blood Submission	X (see Section 14.0)
Patient Questionnaire Booklet	X ²
Booklet Compliance	X ³
End of Active Treatment/Cancel Notification	X
Notification Form – Grade 4 or 5 Non-AER Reportable Events/Hospitalization	At each occurrence (see Section 10.0)
ADR/AER	At each occurrence (see Section 10.0)

1. Complete at each evaluation during Active Treatment (see Section 4.0).
2. Patient questionnaire booklet **must** be used; copies are not acceptable for this submission. To be completed prior to treatment every cycle.
3. This form must be completed only if the patient questionnaire booklet contains absolutely NO patient provided assessment information.

Follow-up Material(s)

CRF	Event Monitoring Phase ¹				
	q. 6 months until PD	At PD	After PD q. 6 mos.	Death	New Primary
Event Monitoring	X ²	X ²	X	X	At each occurrence

1. If a patient is still alive 2 years after registration, no further follow-up is required.
2. Submit copy of documentation of response or progression to the MCCC Operations Office, Attention: XXXXXXXXXX.

19.0 Budget

- 19.1 Costs charged to patient: routine clinical care
- 19.2 Tests to be research funded: amylase and lipase blood tests, Electrocardiograms, ECHOs, Optional Cycle 2, Day 1 tissue biopsy and study drug, ponatinib.
- 19.3 Other budget concerns: none

Appendix I
ECOG Performance Status Scale

SCORE	DESCRIPTION
0	Fully active, able to carry on all pre-disease performance without restriction.
1	Restricted in physically strenuous activity but ambulatory and able to carry out work of a light or sedentary nature, e.g., light housework, office work.
2	Ambulatory and capable of all self-care but unable to carry out any work activities. Up and about more than 50% of waking hours.
3	Capable of only limited self-care, confined to bed or chair more than 50% of waking hours.
4	Completely disabled. Cannot carry on any self-care. Totally confined to bed or chair.
5	Dead.

Name _____

Mayo Clinic No _____

Study Name/Number _____

Appendix II: MEDICATION DIARY

Patient Instructions

- Please indicate on the calendar below *every* day that you take your study medication by placing the dose taken on the line under the date.
- If you miss a dose, place a check “0” under the date, but remember to take your prescribed dose at the next regularly scheduled time.
- Bring *all* bottles and any unused study medication along with this diary when you return for your next appointment.

Medication(s)	Dose
Ponatinib	MG

Study Drug	Day 1	Day 2	Day 3	Day 4	Day 5	Day 6	Day 7
Date							
Ponatinib							

Study Drug	Day 8	Day 9	Day 10	Day 11	Day 12	Day 13	Day 14
Date							
Ponatinib							

Study Drug	Day 15	Day 16	Day 17	Day 18	Day 19	Day 20	Day 21
Date							
Ponatinib							

Study Drug	Day 22	Day 23	Day 24	Day 25	Day 26	Day 27	Day 28
Date							
Ponatinib							

Date: _____

Participants Signature: _____

Area Below Only To Be Completed only by Coordinator

Number of pills returned _____

Study Coordinator Initials _____

Date _____

Discrepancy Yes _____ No _____

